## **6. STUDY OBJECTIVES AND ENDPOINTS**

### **6.1. Primary Objectives**

To provide continuing treatment with bardoxolone methyl as part of this extended access program while collecting ongoing safety and tolerability data of bardoxolone methyl.

### **6.2. Primary Safety Endpoint:**

Frequency, intensity, and relationship to study drug of adverse events (AEs) and serious adverse events (SAEs), and change from baseline in the following assessments: physical examinations, vital sign measurements, BNP, N-terminal pro-brain natriuretic peptide (NT-proBNP), and weight.

## 7. INVESTIGATIONAL PLAN

### 7.1. Overall Study Design

This extended access study will assess the long-term safety and tolerability of bardoxolone methyl in qualified patients with PH who previously participated in controlled clinical studies with bardoxolone methyl.

Qualified patients will start dosing at 10 mg of bardoxolone methyl every other day, then begin once daily dosing at Week 4 (unless contraindicated clinically) and continue the drug for up to 5 years or until patient withdrawal, whichever is sooner. The treatment duration may be extended in a future protocol amendment subject to all applicable regulatory and ethics approvals. Dose de-escalation (down to 5 mg) is permitted during the study if indicated clinically. Refer to [Section 7.3.1](#) for additional details on dose de-escalation.

All patients in the study will follow the same visit and assessment schedule. Patients will be scheduled to be assessed in person during treatment at Day 1, Week 2, Week 4, Week 6, Week 8, Week 24, and every 24 weeks thereafter. Patients will also be assessed by telephone contact on Days 3, 10, 21, 31, and 38. Day 1 for this extended access study should occur on the same day as the last visit in the controlled clinical study. Patient status should be carefully monitored by the investigator during the first 8 weeks of study treatment. Assessments required for both the last visit in the controlled study and Day 1 for this study should only be completed once.

#### Patients from the CATALYST study:

Day 1 of this extended access study will coincide with the Week 28 follow-up visit for patients from CATALYST (402-C-1504, NCT02657356, EudraCT 2016-000196-24). If this extended access program is not yet open for enrollment at the time of a patient's Week 28 visit, the Day 1 visit (*i.e.*, enrollment) must occur within 30 days of site activation. Exceptions allowing CATALYST patients who have completed 24 weeks of treatment to schedule their follow-up assessments prior to Week 28 and still be considered eligible for this open-label study should be discussed with the Chief Medical Officer at Reata, or designee, and will be considered on a case-by-case basis.

#### Patients from the LARIAT study:

Day 1 of this extended access study will coincide with the End-of-Treatment visit for patients from LARIAT (402-C-1302, NCT02036970).

### 7.2. Number of Patients

Patient numbers will be determined by those who have been treatment-compliant and who have previously participated in clinical studies with bardoxolone methyl.

### 7.3. Treatment Assignment

All patients will receive bardoxolone methyl in this study.

### **7.3.1. Dose Escalation and Dose De-Escalation**

Patients will start dosing at 10 mg of bardoxolone methyl every other day, then begin once daily dosing at Week 4 unless contraindicated clinically. The investigator should discuss any reasons for not dose-escalating to once daily dosing at Week 4 with the medical monitor.

Dose de-escalation is permitted during the study and the investigator may choose to decrease the patient's dose to 5 mg if clinically indicated. Reasons for dose de-escalation should be discussed with the medical monitor prior to changing dose. Once a patient's dose has been decreased to 5 mg, they cannot dose-escalate back to 10 mg of bardoxolone methyl.

Unscheduled visits due to dose de-escalation should include assessments detailed in [Section 9.7](#).

### **7.4. Criteria for Study Termination**

The Sponsor reserves the right to discontinue the study at any time for clinical or administrative reasons, or if required by regulatory agencies. If the Sponsor discontinues the study, all study drugs will be discontinued and the investigator will be responsible for securing any alternative therapy to be administered, as appropriate.

### **7.5. Criteria for Premature Termination or Suspension of Investigational Sites**

A study site may be terminated prematurely or suspended if the site (including the investigator) is found in significant violation of Good Clinical Practice (GCP), protocol, or contractual agreement with Sponsor or the site is unable to ensure adequate performance of the study.

### **7.6. Procedures for Premature Termination or Suspension of the Study or the Participation of Investigational Sites**

In the event that the Sponsor, an institutional review board (IRB)/ethics committee (EC), or regulatory authority elects to terminate or suspend the study or the participation of an investigational site, a study-specific procedure for early termination or suspension will be provided by the Sponsor.

### **7.7. Schedule of Assessments**

[Table 3](#) lists the overall schedule of assessments for the study.

**Table 3: Schedule of Assessments**

Assessment \ Study Week (Day)	Day 1 a	Week 1 (Phone) Day 3±2	Week 1 Day 7±3	Week 2 (Phone) Day 10±2	Week 2 Day 14±3	Week 3 (Phone) Day 21±2	Week 4 Day 28±3	Week 4 (Phone) Day 31±2	Week 5 (Phone) Day 38±2	Week 6 Day 42±3	Week 8 Day 56±3	Week 24±3, Every 24 Weeks	End of Study Visit b
Informed consent	X												
Inclusion/Exclusion	X												
Prior and Concomitant medications	X c	X	X	X	X	X	X	X	X	X	X	X	X
Current PAH background medications	X c	X	X	X	X	X	X	X	X	X	X	X	X
Weight at home	X	X	X	X	X	X	X	X	X	X	X		
Weight in clinic	X c		X		X		X			X	X	X	X
Vital sign measurements	X c		X		X		X			X	X	X	X
Physical examination	X c		X		X		X			X	X	X	X
Pregnancy test d	X c											X	
Dispense study drug	X						X					X	
Collect study drug							X					X	X
Telephone contact		X		X		X		X	X				
Adverse event collection	X c	X	X	X	X	X	X	X	X	X	X	X	X
Clinical Chemistries f	X c		X		X		X			X	X	X	X
BNP and/or NT-Pro BNP	X c		X		X		X			X	X	X	X
6-min walk test	X c											X	X
Dyspnea and fatigue g	X c											X	X
WHO functional class	X c											X	X

a On Day 1, all procedures should be performed before study drug administration for patients who are treatment-compliant and have previously participated in clinical studies with bardoxolone methyl.

b After the Week 24 visit, patients will continue to be assessed in person every 24 weeks. The End of Study visit should occur within 30 days after the patient receives their final dose of study medication under this protocol. Patients who will be discontinued from the study prior to the completion of the study must also complete all End-of-Study assessments.

c Day 1 assessments should be performed as part of End-of-Treatment or Follow-up visit procedures from a prior study with bardoxolone methyl.

d A serum pregnancy test will be performed at any point in time if a pregnancy is suspected. All other pregnancy assessments will be urine pregnancy tests. Additional pregnancy assessments will be performed more frequently if required by local law or requested by local health authorities or IRBs/ECs.

e AE assessments on Day 1 should be performed following study drug administration.

f Clinical chemistries will be analyzed locally.

g Dyspnea and fatigue must be assessed prior to beginning and immediately following completion of the 6MWT using the Borg scale.

Abbreviations: PAH, pulmonary arterial hypertension; BNP, B-type natriuretic peptide; NT-proBNP, N-terminal pro B-type natriuretic peptide; WHO, World Health Organization; AE, adverse event; 6MWT, 6-minute walk test.

## **8. SELECTION AND WITHDRAWAL OF PATIENTS**

### **8.1. Patient Inclusion Criteria**

Main criteria for inclusion:

1. Treatment-compliant patients who are participating in qualifying ongoing studies (CATALYST, EudraCT 2016-000196-24; LARIAT, EudraCT 2016-004793-17) and who have completed required End-of-Treatment and/or Follow-up visits in one of these prior clinical studies with bardoxolone methyl and who, according to the assessment of the investigator, have a potential positive benefit-risk assessment for participating in the trial.
2. Evidence of a personally signed and dated informed consent document indicating that the patient has been informed of all pertinent aspects of the study prior to initiation of any protocol-mandated procedures.

### **8.2. Patient Exclusion Criteria**

All patients with any of the following conditions or characteristics must be excluded from the study:

1. Participation in other investigational clinical studies involving interventional products being tested or used in a way different from the approved form or when used for an unapproved indication;
2. Patients who have an ongoing serious adverse event (SAE) from a clinical study that is assessed by the investigator as related to bardoxolone methyl;
3. Unwilling to practice acceptable methods of birth control (both males who have partners of childbearing potential and females of childbearing potential) while taking study drug;
4. Women who are pregnant or breastfeeding;
5. Patient is, in the opinion of the investigator, unable to comply with the requirements of the study protocol or is unsuitable for the study for any reason;
6. Known hypersensitivity to any component of the study drug.

### **8.3. Patient Discontinuation and Termination**

Patients have the right to discontinue study drug or withdraw from the study at any time for any reason, without prejudice to their medical care. Furthermore, the investigator may discontinue a patient from study drug. Consultation with the medical monitor should occur prior to study drug discontinuation or withdrawing a patient from the study. The reason for a patient's discontinuation from study drug or study termination will be recorded in the electronic case report form (eCRF).

Discontinuation refers to a patient's stopping administration of study drug and all study assessments and visits. Reasons for study drug discontinuation may include the following:

- Occurrence of an AE or change in medical status that will lead the investigator to be concerned about the patient's welfare;
- Administrative reasons (*e.g.*, inability to continue);
- Sponsor termination of the study;
- Voluntary withdrawal;
- Females who become pregnant during the study;
- Premature termination or suspension of an investigational site;
- Loss to follow-up;
- Death;
- Withdrawal of consent.

Patients must discontinue study drug if any of the following occur.

- ALT or AST > 8X ULN;
- ALT or AST > 5X ULN for more than 2 weeks;
- ALT or AST > 3X ULN and (total bilirubin > 2X ULN or International Normalized Ratio [INR] > 1.5);
- ALT or AST > 3X ULN with the appearance of fatigue, nausea, vomiting, right upper quadrant pain or tenderness, fever, rash, and/or eosinophilia (> 5%).

Patients who discontinue from the study will be asked to complete the End-of-Study procedures noted in [Table 3](#).

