#### **9.1.2. Management of Elevated Transaminase Levels (ALT and/or AST)**

Transaminases should be monitored following patient's standard of care. Nearly all instances of elevated transaminases are expected to be asymptomatic. Transaminase levels (as well as total bilirubin [TBL], GGT, alkaline phosphatase, and INR) will be checked within 48 to 72 hours during an unscheduled visit if the following occurs:

- ALT or AST levels > 3X ULN.

Testing will be repeated every 72 to 96 hours until transaminase levels are below 3X the ULN for at least one week or until the patient withdraws consent.

Study drug administration will be permanently discontinued if any of the following occurs:

- ALT or AST > 8X ULN;
- ALT or AST > 5X ULN for more than 2 weeks;
- ALT or AST > 3X ULN and (TBL > 2X ULN **or** INR > 1.5);

- ALT or AST > 3X ULN with the appearance of fatigue, nausea, vomiting, right upper quadrant pain or tenderness, fever, rash, and/or eosinophilia (> 5%).

The hepatobiliary tree must be visualized (*e.g.*, ultrasound, magnetic resonance imaging) and assessed if a patient discontinues taking study drug secondary to elevated transaminase levels. Additional tests/studies may be warranted depending on the clinical presentation.

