#### **11.6. Recording Adverse Events**

All conditions present prior to the administration of the first dose of study drug (Day 1) in a previous study with bardoxolone methyl should be documented as medical history in a previous study with bardoxolone methyl. After the first dose, documentation of AEs shall continue until 30 days following administration of the final dose of study medication under this protocol (*i.e.*, through the End-of-Treatment visit), regardless of the relationship of the AE to study drug. Information to be collected will include type of event, date of onset, date of resolution, investigator-specified assessment of severity and relationship to study drug, seriousness, as well as any action taken.

While an AE is ongoing, changes in the severity (*e.g.*, worsening and improving) should be noted in the source documents, but when documenting the AE, only the total duration and greatest severity should be recorded in the eCRF. AEs characterized as intermittent will require documentation of onset and duration.

All drug-related (possibly, probably, or definitely related, see [Section 11.4](#)) AEs and abnormal laboratory test results reported or observed during the study must be followed to resolution (either return to baseline or within normal limits). All other AEs will be followed through the final visit indicated in [Table 3](#), as appropriate.

AEs resulting from concurrent illnesses, reactions to concurrent illnesses, reactions to concurrent medications, or progression of disease states must also be reported. Preexisting conditions (present before the start of the AE collection period) will be considered concurrent medical conditions and should NOT be recorded as AEs. However, if the patient experiences a worsening or complication of such a concurrent condition, the worsening or complication shall be recorded as an AE. Investigators shall ensure that the AE term recorded captures the change in the condition (*e.g.*, “worsening of...”). Any improvement in condition shall be documented per [Section 9.10.7](#).

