6.6.4. Missing Treatment or Study End Date

The study was terminated on March 30, 2020. If the treatment end date or study end date are missing, the date will be imputed as March 30, 2020. If the treatment end date or study end date are missing and no reason for treatment or study discontinuation are included in the CRF, the reason for treatment or study discontinuation will be study termination.

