7.2. Subjects Disposition

A disposition summary includes the number and percentage of patients in the following categories:

- Patients with prior participation in LARIAT
- Patients with prior participation in CATALYST and randomized to placebo (only summarized when unbinding of CATALYST has occurred)
- Patients with prior participation in CATALYST and randomized to bardoxolone methyl (only summarized when unblinding of CATALYST has occurred)
- Continuing (or complete) treatment
- Terminate from the study
 - Reason for terminating study

Results will be summarized by analysis population (Section 6.3). A listing of disposition is provided for all enrolled patients.

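### Protocol 8.3 defines discontinuation as ending drug and all assessments, contrary to 9.1.2, 11.2.1.2 and 11.6, and SAP 7.2 tabulates reasons for leaving the study but not for stopping drug

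*Protocol*

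**What the plan says.** Protocol 8.3 opens with two distinct acts: "Patients have the right to discontinue study drug or withdraw from the study at any time for any reason". It then gives one definition covering both: "Discontinuation refers to a patient's stopping administration of study drug and all study assessments and visits". The list that follows is of reasons for stopping study drug, and the hepatic criteria for mandatory drug stop come after it. The section ends with a visit request: "Patients who discontinue from the study will be asked to complete the End-of-Study procedures noted in" Protocol Table 3. Footnote b of that table puts the End of Study visit within 30 days of the final dose and gives no earliest day.

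Other sections assume that assessments go on after drug is stopped:

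- Protocol 9.1.2, for raised transaminases: "Testing will be repeated every 72 to 96 hours until transaminase levels are below 3X the ULN for at least one week". The only other end point is withdrawal of consent. The same section requires hepatobiliary imaging because drug was stopped for this reason.
- Protocol 11.6 has adverse events documented for 30 days after the final dose. It says that drug-related events and abnormal laboratory results "must be followed to resolution (either return to baseline or within normal limits").
- Protocol 11.2.1.2 requires notification of serious events throughout the study, whether or not the patient is taking drug.

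On reporting, Protocol 8.3 has the reason for stopping drug or leaving the study entered in the eCRF. SAP 6.6.4 handles a treatment end date and a study end date. Where the date is missing and the CRF holds no reason, "the reason for treatment or study discontinuation will be study termination". The SAP 7.2 disposition summary has one treatment-status row without reasons, and a study-termination row broken down by "Reason for terminating study".

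**The concern.** A patient stopped under the hepatic criteria, or for a related adverse event, is one whose course after stopping the protocol says must be followed. If a site takes the 8.3 definition at its word, that is also where assessments stop, apart from the End of Study procedures. Follow-up could then depend on which section a site reads.

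Tolerability is part of the primary objective (Protocol 6.1, SAP 3.1.1), and this is a single-arm descriptive study. How many patients stopped drug, and why, is among the most direct tolerability results it can give. The reason is collected, but the planned disposition summary reports it only at study level.

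**Working it through.** No plan figure is involved, so the check sets the sections side by side and compares day ranges.

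**1. The rules for one patient.** Take a patient whose drug is stopped under the hepatic criteria. By the 8.3 definition, assessments and visits end, with End of Study procedures requested. By 9.1.2, repeat testing continues until values have settled or consent is withdrawn, and imaging is now due. By 11.6, adverse events are recorded to day 30 and related ones are followed without a time limit. The 11.2.1.2 wording presupposes that a patient can be in the study and off drug, which the 8.3 definition excludes. These instructions cannot all be followed as written.

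**2. Whether the End of Study visit closes the gap.** Days are counted from the final dose.

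- Permitted visit days (Protocol Table 3, footnote b): 0 to 30.
- Adverse event recording (Protocol 11.6) and the treatment-emergent limit (SAP 9.1): to day 30.
- Follow-up analysis window (SAP 6.5.5, Table 3): 14 to 35, target 28.
- Overlap of visit and window: max(0, 14) = 14 to min(30, 35) = 30.
- A visit on days 0 to 13 meets the protocol but falls outside the SAP window. That is 14 of the 31 permitted days.
- A visit on day d leaves 30 − d days of the recording period after the last scheduled contact: 30 days if d = 0, and 17 days if d = 13.

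The end of collection is itself stated in two ways. Protocol 11.2.1.1 stops at the final visit in Table 3, which may precede day 30. Protocol 11.6 stops at day 30 and ties that to an End-of-Treatment visit, which Table 3 does not contain. After day 30 no visit is scheduled for a patient off drug, so longer follow-up under 9.1.2 and 11.6 relies on unscheduled contact.

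**3. Where the reason for stopping drug is reported.**

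- Drug stop and study exit are the same event: the study-level reason is also the drug-level reason, and SAP 7.2 has no gap.
- They differ and the cause is an adverse event: SAP 9.1.2 provides a table and a listing.
- They differ and the cause is something else: no summary is planned.

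A hypothetical case shows that the third situation can arise. A patient chooses to stop drug on 10 March 2020. The End of Study visit may fall as late as 9 April (21 days to 31 March, plus 9 = 30). The study is terminated on 30 March, 20 days after the stop. The drug-level reason is the patient's choice, while the study-level reason can be study termination. Only the latter has a place in the table.

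**4. Size.** The documents give no number of patients who stopped drug, by reason or by timing, so no count of those affected can be calculated.

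**The case against.** The best defence is that one general sentence is being set against specific instructions. Sections 9 and 11 carry their own end points, 8.3 itself asks for End of Study procedures, and a sensible site would read 8.3 as ending only the routine schedule. That reading is available. But the sentence says all assessments and visits, and the list beneath it concerns study drug, so the opposite reading is also available. The ambiguity stands.

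A reader might infer more than the documents support:

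- *That post-stop safety data are lost.* They are required by 8.3, Table 3, 11.2.1.2 and 11.6. SAP 9.1 counts events to day 30 and lists later ones, and SAP 6.5.5 has a follow-up window. Nothing shows that collection was in fact cut short.
- *That reasons for stopping drug are lost.* They are in the eCRF. SAP 7.2 lists disposition for all enrolled patients, though without stating the contents, and adverse event stops have their own table. SAP 9.2 also shows exposure and numbers on drug by visit. What is absent is a summary of the other reasons.
- *That SAP 6.6.4 overwrites recorded reasons.* It assigns study termination only when the end date is missing and no reason is in the CRF.
- *That pregnancy stops are hidden.* SAP 9.6 lists every on-study pregnancy.
- *That about 15 to 40 patients are affected.* Protocol 5.2.3 reports 4% to 11% above 3X ULN in clinical studies of the drug. With the SAP ceiling of 366, 0.04 × 366 = 14.6 and 0.11 × 366 = 40.3. That counts patients who would enter repeat testing at full enrolment, not patients who stop drug. The same section says that most elevations resolved on continued drug and that persistent ones above 3X ULN were not seen.

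The two halves of the point also pull against each other: under a literal 8.3 the reporting gap closes. It opens only where drug stop and study exit are treated as separate, as the first sentence of 8.3 and SAP 6.6.4 both allow.

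**Conclusion.** The point holds as an internal contradiction and a reporting gap. Protocol 8.3 contradicts 9.1.2, 11.2.1.2 and 11.6 on what happens after drug is stopped, and a site following its definition may end safety collection early. The End of Study visit is no safeguard, since it can precede both the day-30 limit and the SAP window. In the SAP, non-AE reasons for stopping drug have no planned summary wherever drug stop and study exit differ.

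The consequence is data at risk or unsummarised, not data lost. Its size is unknown. It rests on two assumptions that the documents allow but do not confirm: that some sites apply 8.3 literally, and that for some patients the two events have different reasons. The contradiction should be corrected. No view is taken on which clinical rule should prevail.

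**What to change.** In Protocol 8.3, define discontinuation of study drug and termination from the study as two separate events. Reconcile 8.3 with 9.1.2, 11.2.1, 11.6 and Table 3, so that one rule states which assessments continue after drug is stopped and when collection ends. The content is for the sponsor to decide.

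In SAP 7.2, add a block for patients who discontinued study drug, by the reason recorded in the eCRF. Give stops due solely to the sponsor's termination their own line, so that they are not mixed with individual decisions. Keep study termination by reason alongside it.

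The protocol change is one of wording and need not add visits beyond those that 9.1.2 and 11.6 already require. The SAP change is one table block from a field already collected. The SAP is dated 5 June 2020, after the termination of 30 March 2020, so rewording 8.3 cannot recover anything left uncollected. The disposition block is the part that can still improve the report.

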### **5.2.3. Transaminase and Gamma-Glutamyl Transpeptidase Elevations**

In clinical studies of bardoxolone methyl, almost all patients had increases of transaminase enzymes above baseline upon initiation of treatment, which followed a consistent pattern. These increases were not associated with elevations in bilirubin or other signs of liver toxicity. In a large Phase 3 study that enrolled 2185 patients with type 2 diabetes and stage 4 CKD (BEACON), fewer hepatobiliary SAEs were observed in the bardoxolone methyl arm than in the placebo arm. The elevations begin immediately after initiation of treatment or an increase in dose; they peak approximately two to four weeks later. In most patients, transaminase elevations were mild, but approximately 4% to 11% of patients experienced an elevation greater than 3X the upper limit of normal (ULN). The elevations resolved to levels less than the ULN in most all patients with elevations, within two weeks after peak values while patients continued taking study drug. Patients who experienced elevations to greater than 3X the ULN sometimes required additional time to resolve. While some patients have had elevations to above 3X the ULN, persistent elevations to above 3X the ULN have not been observed, and the elevations did not recur once resolved, unless caused by other factors.

Bardoxolone methyl regulates gamma-glutamyl transpeptidase (GGT), a known Nrf2 target gene. In clinical studies, low level GGT elevations during treatment were common, mild, and typically lasted longer than alanine aminotransferase (ALT)/aspartate aminotransferase (AST) elevations. Bilirubin levels in patients experiencing transaminase or GGT elevations due to treatment with bardoxolone methyl either remained at baseline levels or decreased. The ALT, AST, and GGT elevations were generally self-limiting in patients who continued treatment with study drug.

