#### **9.7. Unscheduled Visits**

Unscheduled visits are allowed for the following reasons:

- Assessment of weight gain per [Section 9.1.1](#);
- Management of an AE or SAE;
- Performance of additional laboratory tests for clinically abnormal laboratory test values or to confirm a possible pregnancy;
- Dose de-escalation;
- Any time the investigator feels that it is clinically appropriate for patient safety.

At a minimum, unscheduled visits should include collection of AEs, concomitant medications and vital signs. Additional conversations may be necessary with the medical monitor following an unscheduled visit to assess patient safety.

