#### **9.10.13. Clinical Chemistry**

Samples will be collected for clinical chemistry analyses as indicated in [Table 3](#). Clinical chemistries will be analyzed locally and should include those routinely monitored per patient's standard of care.

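### Eosinophilia above 5% is part of a mandatory liver stop rule, but no protocol-required test supplies the eosinophil percentage

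*Protocol*

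**What the plan says.** Section 8.3 introduces four hepatic criteria with "Patients must discontinue study drug if any of the following occur". Section 9.1.2 repeats the same four and makes the stop permanent: "Study drug administration will be permanently discontinued if any of the following occurs". The fourth criterion is ALT or AST above 3X ULN with the appearance of fatigue, nausea, vomiting, "right upper quadrant pain or tenderness, fever, rash, and/or eosinophilia (> 5" (the figure is a percentage). The features are joined by and/or, so any one of them is enough.

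Two places in the protocol say which blood tests are required:

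- **Table 3.** The only scheduled blood tests are clinical chemistries and BNP and/or NT-proBNP; a serum pregnancy test is added if pregnancy is suspected. There is no haematology row. A footnote says "Clinical chemistries will be analyzed locally", and section 9.10.13 says the chemistries "should include those routinely monitored per patient's standard of care". SAP Table 2 repeats the schedule without adding a blood count.
- **The work-up in section 9.1.2.** When ALT or AST exceeds 3X ULN, "Transaminase levels (as well as total bilirubin [TBL], GGT, alkaline phosphatase, and INR) will be checked within 48 to 72 hours". Testing is then repeated every 72 to 96 hours until transaminases have been below 3X ULN for at least a week or the patient withdraws consent.

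Section 9.7 allows unscheduled visits for further testing: "Performance of additional laboratory tests for clinically abnormal laboratory test values or to confirm a possible pregnancy". The minimum content of such a visit is adverse events, concomitant medications and vital signs.

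**The concern.** A mandatory stop rule is only as reliable as the measurements that feed it. Here one sufficient condition for stopping is a laboratory value that the protocol never requires anyone to measure. A site could follow every instruction and still not learn that the condition was met.

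Two things are at stake. The first is consistent application: with approximately 150 centres, remote monitoring (section 13.2) and no data safety monitoring committee (section 13.1), whether eosinophils are counted depends on local habit. The second is interpretation: in the study data, no recorded eosinophilia could mean that it was measured and normal, or that it was not measured.

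**Working it through.** The protocol states no figure to reproduce. The check sets each element of the four stop criteria against the test or assessment that the protocol requires.

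| Stop criterion (8.3 and 9.1.2) | Information needed | Required source |
|---|---|---|
| ALT or AST > 8X ULN | transaminases | 9.1.2 work-up |
| ALT or AST > 5X ULN for more than 2 weeks | serial transaminases | 9.1.2 repeats every 72 to 96 hours |
| ALT or AST > 3X ULN with TBL > 2X ULN or INR > 1.5 | TBL and INR | both named in the 9.1.2 work-up |
| ALT or AST > 3X ULN with fatigue, nausea, vomiting, right upper quadrant pain or tenderness, fever or rash | symptoms and signs | adverse event questioning, vital signs or physical examination (9.10.12, 9.10.6, 9.10.7) |
| ALT or AST > 3X ULN with eosinophilia > 5% | differential white cell count | none |

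So six of the seven accompanying features in the fourth criterion have a required assessment and one does not. The panel carries the two tests that the third criterion needs, and also GGT and alkaline phosphatase, which no stop criterion uses. It omits the one laboratory value that the fourth criterion uses.

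**Which patients fall in the gap.** Excluding everyone caught by another mandatory stop leaves patients who meet all of these:

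- ALT or AST above 3X and up to 5X ULN for any duration, or above 5X and up to 8X ULN for no more than 2 weeks;
- TBL no higher than 2X ULN and INR no higher than 1.5;
- none of the six symptoms or signs;
- eosinophils above 5%.

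Section 9.1.2 expects nearly all transaminase elevations to be without symptoms. In such a patient, without fever or rash, eosinophilia is the only feature that could trigger the fourth criterion.

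**An upper-end illustration of how many would enter the work-up.** Section 5.2.3 reports that "approximately 4% to 11% of patients experienced an elevation greater than 3X the upper limit of normal (ULN". SAP section 4.3 caps enrolment at 366: 200 from CATALYST and 166 from LARIAT.

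- All 366: 366 × 0.04 = 14.6 and 366 × 0.11 = 40.3, so about 15 to 40 patients.
- CATALYST ceiling only: 200 × 0.04 = 8 and 200 × 0.11 = 22 patients.

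These figures count work-ups, not patients affected. They also assume full enrolment and that the 5.2.3 range carries over. Section 5.2.3 ties the elevations to starting treatment or raising the dose and says that they did not recur once resolved unless caused by other factors. All LARIAT patients, and CATALYST patients randomised to active drug, had prior exposure (SAP section 4.5). All patients do begin on alternate days and step up to daily dosing at Week 4, so elevations in those already exposed cannot be ruled out, but the documents give no rate for them. They also give no rate for isolated eosinophilia, so the number actually in the gap cannot be calculated.

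**The case against.** The strongest reply is that the protocol permits the missing test. ALT or AST above 3X ULN is an abnormal value, section 9.1.2 places the work-up at an unscheduled visit, and section 9.7 allows additional laboratory tests there. Section 9.1.2 also says that further tests may be warranted. That sentence follows the one on patients who have already stopped for transaminases, but nothing in its wording limits it to them. A count may also exist from standard of care. This stands in part: a reader might infer that the criterion cannot be evaluated, and the documents do not support that. Six features are assessable and the seventh can be tested at discretion. What remains is that a mandatory rule rests on an optional test.

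A reader might also infer that drug will be continued in patients who should stop, or that everyone between 3X and 8X ULN is exposed to the gap. Neither follows. Sites may order a count, the investigator may stop drug at any time under section 8.3, and the separate stop above 5X ULN for more than 2 weeks narrows the range.

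Finally, no planned output uses eosinophil counts. The SAP summarises reasons for leaving the study (section 7.2) and adverse events leading to discontinuation (section 9.1.2), but nothing by hepatic stop criterion. The SAP also records that the study was terminated on 30 March 2020 (section 6.6.4), so an amendment could no longer change patient management here. Both points are correct. They limit the practical reach but do not remove the inconsistency or the limit on what the report can say.

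**Conclusion.** The point holds as an internal inconsistency of modest size. One of seven sufficient features in a mandatory, permanent stop criterion has no required measurement in Table 3 or in the work-up triggered above 3X ULN. The consequences are possible uneven application across sites and a possible missed stop in a patient whose only accompanying feature is eosinophilia, within the limits set out in the working.

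The number affected is not given and is probably small. The range of 15 to 40 should not be read as patients harmed or missed: it is an upper-end count of work-ups under full enrolment and an assumed carry-over of the 5.2.3 range. The conclusion rests on the text of the documents alone and does not depend on that range. No sample size, power or error rate is involved, since the study is descriptive. Nothing here judges whether the eosinophilia criterion itself is clinically right.

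**What to change.** Reconcile the stop lists in sections 8.3 and 9.1.2 with the section 9.1.2 work-up panel and Table 3. Either every laboratory element of a mandatory stop criterion has a required measurement recorded in the eCRF, or the lists and the panel are otherwise brought into agreement. Which way to go is the sponsor's clinical decision.

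The cost is small in either direction. If the element stays, the change is a line in the work-up, an eCRF field and a local count taken with a draw that already happens, with no added visit. If it does not, one item comes out of two lists.

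Because the study has been terminated, the step that still applies is in reporting. The clinical study report should state that eosinophil percentage was not a required measurement, and should not treat absence of recorded eosinophilia as evidence that the criterion was checked and not met. The protocol text should be reconciled before it is reused.
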